 - The first day of testing will occur in the MRI simulator room at the Waisman Laboratory for Brain Imaging and Behavior.
 - Psychophysical pain testing will occur during this session, both before and during the MRI simulation procedure.
 - The cognitive task will be introduced and subjects will be permitted to practice the task. This same task will be employed during the MRI simulation as well as actual scans.
- **Physical Activity Assessments**
 - During the week prior to Day 2 participants will wear an activity monitor which will record intensity and frequency of physical activity
- **Participants are assigned to their experimental condition, either RET or WLC**
 - Participants assigned to the RET group will work with study staff to schedule their training sessions for the 16-week trial.
 - Participants assigned to the WLC group will be instructed to maintain their current level of physical activity and exercise for the 16-week trial.

◆ **Day 2 of Testing**

- **Baseline psychophysical, cognitive and functional brain imaging (to occur within 2 months of the first day of testing)**
 - fMRI data collection during psychophysical pain testing and cognitive performance tasks will occur in the 3T MRI room at the Waisman Laboratory for Brain Imaging and Behavior.

◆ **16-Week Trial (will start approximately 1 week after Day 2)**

- **RET group members will attend twice-weekly training sessions (90 minutes) with a personal trainer at the VA Physical Therapy clinic**
- **Outside of test days, WLC group members will go about their typical daily routine**
- **Both groups will complete a small battery of clinical symptom questionnaires on a weekly basis either at home (WLC) or just prior to a training session (RET)**

◆ **Blood Sampling**

- **RET group members will have blood samples drawn one hour before and thirty minutes following their first training session of the week during weeks 2, 7, and 15.**
 - Total volume of blood drawn over the duration of the study for participants in the RET group will be 240 ml.
- **All blood draws will be conducted by a certified phlebotomist who is also a member of the study staff.**
- **Blood draws will take place in the Exercise Psychology Laboratory at the University of Wisconsin-Madison.**

◆ **Days 3, 4 and 5 of Testing**

- **Psychophysical, cognitive and functional brain imaging data will be collected at weeks 6 and 11 of the 16-week trial and one week after completion (week 17)**

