Our experience and data in CMP patients show that MRI habituation procedures are effective to screen for claustrophobia, deliver relative pain stimuli, enhance task performance and minimize subject motion. MRI habituation will take place in the MRI simulator at Waisman. This will entail being placed in a mock MRI unit, trained to rate painful stimuli, and perform the cognitive tasks (Stroop) using the same equipment that will be used in the 3T MRI unit. Pain psychophysics are also conducted and used to calculate the temperature designed to elicit moderate pain ratings. We have found that by habituating subjects they report feeling more at-ease in the MRI which should enhance measurement reliability. Our motion parameters indicate that by habituating subjects' data loss due to motion artifact is limited. In our FM study, quality data analyses indicate that only 6 of 100 subjects had motion exceeding 3 mm. The mock MRI is virtually identical to the actual MRI including fed-in scanner noise. Subjects practice with a scanner-compatible button-press response unit (Current Designs Inc., PA) while viewing stimuli through MRI compatible goggles.

Physical Activity Assessment

Baseline physical activity assessment will occur for one week prior to baseline brain imaging using an accelerometer. Physical activity will also be assessed for one week prior to each testing session. Subjects will be given instructions on the proper use of the accelerometer and will be asked to wear it as much as possible, unless sleeping, bathing or swimming, for the week preceding their baseline assessment.

Baseline Assessment and 16-Week Trial (RET vs. WLC)

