Power estimates for the trial are based on Specific Aim 1. General multivariate regression models will be used to estimate the time averaged difference in pain ratings and clinical symptom scores (continuous measurements) between the treatment and the control group. With general multivariate regression models we model both the dependence of the response on the explanatory variables as well as the autocorrelation among the responses. In order to achieve 90% power, at alpha equal to .05, with an effect size of .6 (minimum effect size of clinical importance) and with a correlation of .6 between measurements from each individual, the necessary sample size would be 34 subjects per group. If we take into account a 20% subject attrition rate, then the total sample size should be 41 subjects per group. All randomized subjects will be included in the analysis within the appropriate arm that they were randomly assigned (i.e. an intent-to-treat analysis will be used). Noncompliance, protocol deviations, withdrawal or any other problem that occur after randomization will be ignored and the participant's last observed data points will be carried forward in the analyses. Missing data will be assumed to be missing completely at random and appropriate missing data methods will be used (i.e. multiple imputation) to minimize the effect of withdrawal. For the purpose of evaluating Specific Aim 2, a similar methodology will be employed to estimate the time averaged difference in physical activity counts as measured by accelerometry.

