To estimate the impact of RET on BOLD responses to pain stimuli we will use a two-sample Hotelling's T-square approach. This will test differences in the vector of means of BOLD response from pain stimuli for the control and exercise group between the baseline (before treatment) and end of the study (after treatment) for three different brain regions (anterior cingulate, insula and middle frontal cortices). These regions were chosen based on the robust brain responses observed in patients with CMP. Hotelling's T-square is a generalization of the Student's t statistic that is used in multivariate hypothesis testing. If there are q variables, the null hypothesis is that the means of variables in the first population equal the means of variables in the second population. For each subject in each group the difference between baseline value and end of the trial value for all brain regions will be computed and a Hotelling's T-square will be performed to compare the mean difference vectors for each group. With a sample size of 34 subjects we will have 80% power to detect a moderate effect size ($\sim .6$), in the treatment group, between baseline and the end of the trial.

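### The Aim 3 BOLD test needs a baseline and an end scan, but the plan does not say how a missing scan is handled, and its imaging power allows for no loss

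*Combined protocol and SAP*

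**What the plan says.** All references are to the Combined protocol and SAP.

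- **Test.** Under Statistical Considerations, for BOLD responses to pain, "we will use a two-sample Hotelling's T-square approach". The regions are the anterior cingulate, insula and middle frontal cortices. The input is the change score: "For each subject in each group the difference between baseline value and end of the trial value for all brain regions will be computed". This paragraph has no rule for a missing or unusable scan.
- **Power.** The same paragraph states: "With a sample size of 34 subjects we will have 80% power to detect a moderate effect size" of about 0.6. It places that effect within the treatment group, from baseline to the end of the trial.
- **Missing data.** The Aim 1 paragraph of that section says "All randomized subjects will be included in the analysis within the appropriate arm that they were randomly assigned". It then names two methods: carrying the last observation forward, and multiple imputation with data assumed missing completely at random. A similar methodology is promised for Aim 2. Aim 3 is not mentioned.
- **Loss.** The Aim 1 sample size continues "If we take into account a 20% subject attrition rate", and arrives at 41 per group. Under Subjects, 34 per group are randomized.
- **Scans.** Study Schedule places scans at baseline, at weeks 6, 11 and 17, and at two later follow-ups. Assignment to a group comes before the baseline scan.
- **Motion.** Day 1 (Screening Day) reports that in the investigators' earlier fibromyalgia study "only 6 of 100 subjects had motion exceeding 3 mm". This is offered as evidence that data loss is limited.

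**The concern.** A change score in three regions exists only for a participant with usable scans at both ends. The plan expects a fifth of participants to be lost, and it does not say what the T-square does with them. Three routes are open, and they do not estimate the same thing. If leaving the trial is related to an early response, a comparison of completers is biased. Carry-forward freezes a response that is meant to build up over 16 weeks. The week 6 and week 11 scans carry information about those who leave, yet the test as written does not use them, although the Summary of Experimental Design presents repeated measurement as a critical feature.

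The power statement is a second, separate problem. It takes the full randomized number as the number analysed, and it describes a within-group change although the planned test compares two groups.

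**Working it through.** **Inputs from the plan:** 34 randomized per group, 20% attrition, three regions, effect about 0.6. **Assumed:** alpha .05 (stated for Aim 1 and not restated for imaging), and all attrition falling before week 17.

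**1. Reproducing the stated 80%.** A one-sample (within-group) Hotelling's T-square has noncentrality n × D² on (3, n − 3) degrees of freedom. With n = 34 and D = 0.6 this is 34 × 0.36 = 12.24 on (3, 31), and power is 0.795. The figure reproduces with all 34 scored.

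**2. Number with an end scan.** 34 × 0.80 = 27.2, about 27 per group.

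**3. Power at a joint distance of 0.6.** The two-sample T-square has noncentrality (n/2) × D² on (3, 2n − 4) degrees of freedom. At 34 this is 17 × 0.36 = 6.12 on (3, 64). At 27 it is 13.5 × 0.36 = 4.86 on (3, 50).

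| Scored per group | Within-group | Two-sample |
|---|---|---|
| 34 | 0.795 | 0.50 |
| 27 | 0.67 | 0.40 |
| 24 | 0.60 | 0.35 |

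The last row adds an assumption that is not in the plan: each of the two scans is unusable with probability 6%, independently of the other and of attrition. Then 27.2 × 0.94² = 24.0.

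**4. If 0.6 is meant in each region.** With a common inter-region correlation r, D² = 3 × 0.36 / (1 + 2r). At r = .3 (an assumption; the plan gives none), D² = 1.08 / 1.6 = 0.675. Two-sample power is then 0.80 at 34, 0.68 at 27 and 0.62 at 24.

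**5. Effect of the missing-scan rule.** This is an illustration by simulation, and every input is an assumption:

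- correlation .6 between visits;
- mean RET change 0, -.2, -.4 and -.6 SD at baseline and weeks 6, 11 and 17, with no change in WLC;
- 20% of RET leave after week 6, selected on a poor week-6 change plus noise of equal variance;
- 20% of WLC leave at random after week 6.

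The true difference is -0.60.

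| Handling | Estimate, correlation .6 | Range, correlations .4 to .8 |
|---|---|---|
| Completers only | -0.71 | -0.73 to -0.68 |
| Carry-forward from week 6 | -0.43 | -0.41 to -0.46 |
| Conditioning on baseline and week 6 | -0.60 | -0.60 throughout |

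Carry-forward is biased even when dropout is random in both groups: 0.80 × (-0.60) + 0.20 × (-0.20) = -0.52.

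**The case against.** The strongest reply is that the section already provides for everyone: all randomized participants are analysed, and carry-forward and imputation are both named. If those rules reach Aim 3, nobody with a baseline scan is dropped. Carry-forward would take a week 6 or week 11 scan as the end value, and imputation could use both. This stands as far as it goes. A reader might infer that the plan commits to a completers' analysis, or that it must overstate the RET effect. The documents support neither. The BOLD paragraph does not say that it drops anyone, and the direction of bias depends on the rule: away from zero for completers, towards zero for carry-forward, and absent in the illustration when the week 6 scan is conditioned on. The reply does not settle which rule applies, because the two methods differ and neither is extended to Aim 3.

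A reader might also infer that the plan's own figures put up to 29% of participants beyond scoring (1 − 0.80 × 0.94² = 29.3%). Only the 20% is a plan figure. The 6 of 100 counts subjects, not scans, in another study, and 3 mm is not stated as an exclusion limit.

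The power loss could be attributed to the clash between 34 randomized and 41 called for. That is partly right. With 41, about 33 would remain (41 × 0.80 = 32.8), and within-group power would be 0.78. But 34 is the number to be randomized, and at 33 the two-sample test at a joint distance of 0.6 still has only 0.49. The fall from 0.80 to 0.50 comes from comparing groups and from taking 0.6 as a joint distance, not from missing scans.

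The Aim 3 section also plans random coefficient mixed models for BOLD together with the diffusion measures. Their time points are not stated, so the remark about unused scans applies to the T-square only.

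**Conclusion.** The point holds in two parts. First, the plan does not say how a participant without a usable pair of scans enters the Aim 3 test, and the open choices lead to materially different answers: about -0.71, -0.43 or -0.60 against a truth of -0.60 in a scenario whose dropout pattern is assumed. Second, the imaging power statement is wrong as written. It describes a within-group test with no loss. At the plan's own 20% attrition, taken as falling before week 17, about 27 per group have an end scan. Power is then about 0.67 within group, or 0.40 for the planned two-sample test at a joint distance of 0.6. If 0.6 is meant per region and the inter-region correlation is .3, it is 0.68. None of the Aim 1 missing-data rules restores the stated 80%. Aim 3 is mechanistic and trial power is set on Aim 1, so this should be corrected but does not touch the primary efficacy analysis.

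**What to change.** 1. **Power.** Restate it for the two-sample comparison at the expected number scored, about 27 per group and lower if scans are lost to motion. Say whether 0.6 applies to each region or is a joint distance; if per region, give the assumed inter-region correlation. For an analysis that also uses partial data, the figure at complete pairs is a cautious approximation.
2. **Analysis.** For Aim 3, rule out completers-only and carry-forward. Either fit a likelihood-based mixed model to all usable scans at baseline and weeks 6, 11 and 17, with a joint 3-df test of the week-17 group differences, or keep the T-square after multiple imputation that uses the week 6 and week 11 scans. The covariance should be parsimonious, for example a separable region-by-visit structure. A fully unstructured one for 3 × 4 = 12 responses has 12 × 13 / 2 = 78 parameters for 68 participants. Report how many randomized participants have no usable scan.
3. **Motion.** Fix the rule for an unusable scan before unblinding, and treat such scans as missing.

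The cost is new analysis wording, somewhat more modelling, a covariance or imputation assumption to defend, and a less favourable stated power. No further scans are needed.

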Hypothesis 1: GV's with CMP assigned to RET will show statistically significant and clinically meaningful improvements in self-reported pain, physical function and PGIC compared to WLC. We also expect significant improvements in the secondary outcomes known to change after exercise training (e.g. sleep, self-esteem, fatigue, anxiety and depression).

Aim2: To determine the influence of RET on total daily physical activity levels using complementary subjective self report and objective measures (accelerometers).

Hypothesis 2: GV's with CMP assigned to RET will show an increase in total physical activity by the end of the trial that is attributable entirely to an increase in RET.

Aim 3: To determine the influence of RET on brain mechanisms of pain **sensitivity** and **regulation** in GV's with CMP compared to WLC. Brain responses to painful heat stimuli will be measured using fMRI. Pain sensitivity will be determined by exposing participants to mild, moderate and strong pain stimuli. Pain regulation will be determined by having the participants perform attention-demanding cognitive tasks while receiving moderately painful stimuli.

Hypothesis 3A (Pain Sensitivity): GV's assigned to RET will show decreased ratings and decreased brain responses to experimental pain stimuli by the end of the treatment trial compared to baseline.

Hypothesis 3B (Pain Regulation): By the end of the treatment trial, GV's assigned to RET will show **decreased** brain responses in areas that process the sensory aspects of pain (e.g. cingulate & sensory cortices), and **increased** brain responses in areas that modulate or inhibit pain when diverting their attention away from a painful stimulus compared to baseline.

Aim 4: To determine the influence of RET on pain-relevant brain white matter tracts in GV's with CMP compared to WLC by conducting DTI analyses of white matter tracts from the thalamus to regions of the brain involved in pain processing and control (e.g. insula, periaqueductal gray, frontal and cingulate regions).

Hypothesis 4A: GV's assigned to RET will show improvements in white matter (measured as increased fractional anisotropy and/or decreased mean diffusivity) compared to baseline.

Research Design and Methods

Pilot subjects:

Five healthy adults (ages 18-60) will be recruited for a single MRI scanning session.

Screening and exclusion criteria for pilot subjects:

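### The 80% power given for the Aim 3 BOLD analysis describes a within-RET change, not the planned two-sample Hotelling's T-square between RET and WLC

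*Combined protocol and SAP*

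**What the plan says.** All of this is in the combined protocol and SAP.

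- **Planned test (Statistical Considerations, BOLD paragraph).** For the effect of RET on BOLD responses, "we will use a two-sample Hotelling's T-square approach". Each subject's baseline-to-end difference is computed for the anterior cingulate, insula and middle frontal cortices, and "a Hotelling's T-square will be performed to compare the mean difference vectors for each group". This is a between-arm test on three change scores.
- **Power sentence (end of the same paragraph).** "With a sample size of 34 subjects we will have 80% power to detect a moderate effect size", given as about 0.6, "in the treatment group, between baseline and the end of the trial". The number is 34 subjects, with no mention of a per-group count. The Aim 1 calculation in the preceding paragraph does give its 34 per group.
- **Aims and hypotheses (Specific Aims and Hypotheses).** Aims 3 and 4 set RET against WLC. The hypotheses under them set RET against its own baseline: 3A expects "decreased brain responses to experimental pain stimuli by the end of the treatment trial compared to baseline", 3B is worded likewise, and 4A expects "increased fractional anisotropy and/or decreased mean diffusivity) compared to baseline". Hypothesis 1, in contrast, is worded against WLC.
- **Not stated for this test.** The alpha, what an effect size of 0.6 means for a vector of three regions, the correlation between regions, and the number evaluable after dropout. The alpha of 0.05 and the 20% attrition both appear in the Aim 1 calculation only.

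**The concern.** The test and the power statement describe different contrasts. A pre-post change in one arm carries the sampling error of one mean vector. A difference in change between two arms of the same size carries the error of two, so at the same standardised distance the noncentrality is halved. A power figure for the first therefore cannot be read across to the second.

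What is at stake is how Aim 3 is read. If the planned comparison has materially less than 80% power, a null BOLD result could be taken as evidence that RET has no neural effect when the test had little chance of showing one. The hypothesis wording adds to the confusion, because the one-arm power sentence fits Hypotheses 3A and 3B as written but fits neither Aim 3 nor the analysis.

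**Working it through.** **Inputs.** From Statistical Considerations: p = 3 regions, 34 subjects, effect about 0.6, stated power 80%. From the Subjects section: 34 per group. Assumed, because the documents do not say: alpha 0.05; 0.6 is the Mahalanobis distance D of the mean change vector (D² = 0.36); no mean change in WLC, so that the within-RET effect equals the between-arm effect; and a common covariance of the change scores in both arms.

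**Step 1: reproduce the plan's figure as a one-sample test.**
Reference distribution F(p, n − p) = F(3, 31), critical value 2.91. Noncentrality λ = n·D² = 34 × 0.36 = 12.24. Power = **79.5%**, which is the stated 80%. A 20,000-replicate simulation also gave 79.5%.

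**Step 2: same inputs, planned two-sample test.**
Reference distribution F(p, n₁ + n₂ − p − 1) = F(3, 64), critical value 2.75. λ = [n₁n₂/(n₁ + n₂)]·D² = 17 × 0.36 = 6.12, half the value above. Power = **50.0%** (simulation 49.6%).

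**Step 3: what 80% would take.** At 34 per arm, D must be about 0.83. At D = 0.6, 63 per arm would be needed (80.3%).

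**Step 4: an attrition scenario.** If 34 per arm are randomised and 20% are lost, 34 × 0.8 = 27.2, so about 27 per arm are evaluable. λ = 13.5 × 0.36 = 4.86 and power is about **40%**; 80% would need D of about 0.93. This is a scenario, not a prediction.

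**Step 5: 0.6 read as a per-region effect.** With 0.6 in each region, all of the same sign, and a common correlation ρ between regions, D² = 3 × 0.36/(1 + 2ρ). Two-sample power at alpha 0.05:

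| ρ | D² | 34 per arm | 27 per arm |
|---|---|---|---|
| 0 | 1.08 | 95% | 88% |
| 0.3 | 0.675 | 80% | 68% |
| 0.5 | 0.54 | 69% | 57% |
| 0.7 | 0.45 | 60% | 49% |

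On this reading the planned test reaches 80% at 34 per arm only if ρ is about 0.3 or less. The one-sample test would then have 97.6% at ρ = 0.3 and 93.6% at ρ = 0.5, so the 80% would no longer match the contrast that the sentence names.

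**Step 6: other routes to about 80%.** A one-sided, single-variable two-sample t-test at 34 per group gives 78.9%, but it is not the planned test. Neither that nor the ρ = 0.3 case fits a sentence about change within the treatment group. The one-sample T-square fits both the wording and the number.

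**The case against.** The best defence is that 50% is not a property of the plan. The paragraph says only that the effect is moderate, about 0.6, and a reader is free to take that as an effect in each region. The Mahalanobis distance cannot be smaller than the largest single-region standardised difference, so on any per-region reading 50% at 34 per arm is the floor, and at correlations of 0.3 or below the planned test meets or passes 80%. This stands: an unqualified statement that the BOLD test has 50% power would go beyond the documents. It does not rescue the sentence, which still names the wrong contrast and states no correlation.

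A reader might also infer from the hypotheses that the control arm would go unused, so that habituation to repeated heat pain and scanning would be credited to RET. The documents do not support this for BOLD. The specified test does compare the two arms' change vectors, so habituation common to both arms cancels, and Aims 3 and 4 both name WLC as the comparator. What remains is loose hypothesis wording.

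Two further limits stand. Hypothesis 4A concerns DTI measures; the power sentence covers BOLD only, and the plan analyses FA and MD jointly with BOLD through random coefficient mixed models. So 4A shares the wording problem but not the power problem. And the 27-per-arm scenario is open to argument: the Aim 1 text inflates to 41 per group while the Subjects section randomises 34, and the plan intends to analyse everyone randomised using carried-forward or imputed values.

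**Conclusion.** The point holds as a mismatch between contrast and test. The 80% is not a calculation slip; it is right, to within rounding, for a one-sample T-square on change within RET. It is not power for the two-sample comparison that the plan specifies, and the documents do not contain that figure.

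Its size depends on inputs the plan leaves undefined. With alpha 0.05, no mean change in WLC and 0.6 as the multivariate distance, the planned test has about 50% power at 34 per arm. With 0.6 in every region and the same sign, it runs from about 95% down to 60% as the correlation goes from 0 to 0.7.

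A reader might go on to conclude that the trial as a whole is underpowered. That does not follow from this point: the plan bases trial power on Aim 1, and nothing here alters the Aim 1 calculation. The consequence is confined to the mechanistic Aim 3. This should be fixed, but it does not threaten the primary analysis.

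**What to change.** 1. Replace the BOLD power sentence with power for the two-sample Hotelling's T-square. State alpha, how the effect size is defined for three regions, the assumed between-region correlation (or that 0.6 is the Mahalanobis distance), and the evaluable number per arm. For example, at alpha 0.05 and 34 per arm: about 50% at distance 0.6, or 80% at distance about 0.83, with a second figure for the number expected after dropout.
2. Word Hypotheses 3A, 3B and 4A as RET-versus-WLC differences in change, in line with Aims 3 and 4, and label within-RET change as descriptive. For BOLD this only aligns the wording with a test that is already controlled.

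The cost is protocol text and probably a less favourable stated power for Aim 3. No new data, procedures or participants are needed.

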Once they are enrolled, pilot subjects will be screened during a face-to-face interview with a member of the study staff. Pilot participants will be screened to ensure that they are not color-blind, claustrophobic, or have metal in their body. Female pilot subjects who are pregnant, planning on becoming pregnant, or who cannot confirm they are not pregnant will not be eligible. Pregnancy status will be obtained at two levels of our experimental procedures. First, we will ask that they read and sign a statement at the end of the consent document confirming that they are not pregnant. Second, our MRI technicians will ask all female subjects to confirm that they are not pregnant prior to entering the scanner for each scan.

Subjects:

Sixty-eight U.S. military veterans of the Gulf War (1990-1992) with chronic musculoskeletal pain (**ages 35-65 yrs**) will be recruited and randomly assigned in blocks (to ensure 34 participants in each group) using the Research Randomizer tool (randomizer.org) to 16 weeks of RET or WLC.

Screening and exclusion criteria:

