Secondary analyses may also be conducted on particular brain regions or a set of brain regions (known as a mask) as defined by the Harvard Oxford Atlas. Estimates of voxel-based power, determined by detecting moderate signal changes (0.5% to 1.5%) and basing power on a noncentral t-distribution method, indicate that for most brain regions of interest a sample size of 12 subjects per group in the 'pain' condition provides power of 0.8 for rejecting the null hypothesis at an uncorrected α of .005 assuming robust pain-related activity (signal change $\sigma_B=0.3\%$), a moderate difference level for groups and greater than 100 time points in the 'pain' condition (69). Our preliminary data from our NIH project indicate robust responses to our experimental manipulations with sample sizes as small as 5 ($n=5$ RA group, $n=11$ Con, $n=14$ FM). For group comparisons, our preliminary NIH data indicate large effects between groups for FM patients compared to controls in several hypothesized regions. Significant differences ($p<0.01$) between patients and controls for the 'pain' condition occurred in several regions including the IC ($t=3.6$) and frontal cortex (BA 10; $t=3.7$). For the pain plus distraction condition we found significant differences ($p<0.01$) in several regions including the orbitofrontal (Con > FM, $t=3.3$) and IC (FM > Con, $t=3.5$). Effect sizes (d) for these differences ranged from 1.36 to 1.53. Assuming an α of 0.01 and a conservatively large effect size of $d=0.80$, 11 subjects per group would provide power of 0.9 to detect differences in the Main Effect for either pain or pain plus distraction conditions. Therefore our sample sizes of 12 per group should provide sufficient power to detect significant differences when they are present.

To study the joint effect of the BOLD response values as well as FA and MD values from DTI measurements, random coefficient mixed models will be used. Random coefficient mixed models assume that the regression coefficients are a random sample from a population of possible coefficients and allows modeling the variation between the study units (70). As in the case with multiple response variables (multiple brain regions), a separate set of regression coefficients will be fitted for each response variable and the correlation among these random coefficients can be examined.

Data and Record Keeping

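### The secondary imaging power figure of 0.9 at 11 per group (d = 0.80, alpha 0.01) is about 0.20 for a two-group test, and 12 per group is not this trial's arm size

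*Combined protocol and SAP*

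**What the plan says.** The point lies in the Statistical Considerations section, in the paragraph on secondary analyses of particular brain regions or masks. That paragraph presents these analyses as ones that may be done.

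- It turns to between-group effects with pilot data: "For group comparisons, our preliminary NIH data indicate large effects between groups for FM patients compared to controls in several hypothesized regions". The pilot groups relevant here are 14 fibromyalgia patients and 11 controls, with t values from 3.3 to 3.7. It adds: "Effect sizes (d) for these differences ranged from 1.36 to 1.53".
- It then takes alpha 0.01 and a smaller d of 0.80, described as conservative, and states that "11 subjects per group would provide power of 0.9 to detect differences in the Main Effect for either pain or pain plus distraction conditions".
- It closes: "Therefore our sample sizes of 12 per group should provide sufficient power to detect significant differences when they are present".

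Elsewhere the size is different. Under Subjects, 68 veterans "will be recruited and randomly assigned in blocks (to ensure 34 participants in each group". The Aim 1 power calculation gives 34 per group as needed and 41 per group once 20% attrition is allowed for. The Hotelling's T-square paragraph also uses 34. Apart from the voxel-based estimate in the same paragraph, the only other 12 is the cohort size, which is 6 per condition.

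**The concern.** At alpha 0.01, 11 people per group is far too few to give 0.9 power for a standardised difference of 0.80 between two groups. The paragraph's own numbers raise the doubt: it needed effects of 1.36 to 1.53 to reach p < 0.01 with 14 and 11 people, yet it claims 0.9 power for an effect little more than half that size with no more people. The closing sentence then calls 12 per group our sample sizes, although the arms have 34.

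What is at stake is how these imaging comparisons would be read. A reader who trusts the sentence could take a non-significant regional result as informative when, for d = 0.80, the comparison would usually miss a true effect.

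**Working it through.** **Inputs (all from Statistical Considerations unless stated).** Alpha 0.01; d = 0.80; n = 11 per group; stated power 0.9; concluded n = 12 per group; pilot d 1.36 to 1.53; 34 per arm (Subjects, and Aim 1 power); 41 per arm with attrition (Aim 1 power); correlation 0.6 between measurements (stated for Aim 1 only). Sidedness is not stated. Two-sided is used as an assumption, and one-sided is also shown.

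**What d means here.** The pilot t values convert to d in two usual ways:

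- t × √(1/11 + 1/14): 3.3 gives 1.33 and 3.7 gives 1.49.
- 2t/√23: 3.3 gives 1.38 and 3.7 gives 1.54.

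These agree closely with the stated range of 1.36 to 1.53, so the plan's d is the ordinary between-group standardised difference.

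**Formula.** For a two-sample t-test with n per group, the degrees of freedom are 2n − 2 and the noncentrality is λ = d√(n/2). Power is the probability that a noncentral t with these parameters exceeds the critical value in absolute terms.

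**Attempt to reproduce 0.9.** With n = 11, λ = 0.80 × √5.5 = 1.876, df = 20, and the two-sided 1% critical value is 2.845. The expected test statistic lies well below the critical value, so power is 0.197. A hand check by the normal approximation: Φ(1.876 − 2.576) = Φ(−0.700) = 0.242.

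Other readings with n = 11 and d = 0.80:

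| Reading | Power |
|---|---|
| Two-sample t, two-sided, alpha 0.01 | 0.197 |
| Two-sample t, one-sided, alpha 0.01 | 0.282 |
| Normal approximation, one-sided, alpha 0.01 | 0.326 |
| Two-sample t, two-sided, alpha 0.05 | 0.431 |
| Paired or one-sample, n = 11, alpha 0.01, two-sided (one-sided) | 0.362 (0.488) |
| Between-group mean of 2 to 9 measures, correlation 0.6, alpha 0.01, two-sided | 0.26 to 0.33 |

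For the repeated-measures row, d is divided by √[(1 + (m − 1) × 0.6)/m]. With m = 2 this gives 0.80/√0.8 = 0.894 and power 0.26.

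None of these reproduces 0.9.

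**What would be needed.** The normal approximation gives n = 2(2.576 + 1.282)²/0.80² = 46.5, so 47 per group. The exact t calculation gives 49 (43 one-sided).

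**Power at other sizes and effects (two-sided, alpha 0.01).**

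| n per group | d = 0.80 | d = 1.36 | d = 1.53 |
|---|---|---|---|
| 11 | 0.197 | 0.636 | 0.762 |
| 12 | 0.223 | 0.692 | 0.812 |
| 27 | 0.606 | 0.988 | 0.998 |
| 34 | 0.739 | 0.998 | above 0.999 |
| 41 | 0.834 | above 0.999 | above 0.999 |

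The 27 is 34 × 0.8 = 27.2, rounded down. It assumes that the 20% attrition falls on the 34. The 41 is the plan's own inflated figure (34 × 1.2 = 40.8), taken here as the number analysed.

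**Effect detectable with 0.9 power:** d = 1.80 at 11 per group, 1.71 at 12, and 0.96 at 34.

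**The case against.** **The test is not named.** The sentence speaks of a main effect for a condition and gives no test, sidedness or correlation. A within-subject condition effect pooled over all 22 people can come close to 0.9. With two conditions, f = 0.4 (half of d) and correlation 0.6, the noncentrality is 0.16 × 22 × 2/0.4 = 17.6 and power is 0.897. A one-sample test on 22 people gives 0.81 two-sided and 0.88 one-sided. This stands as a reason to ask which test was meant. It does not rescue the sentence as written: the passage is introduced as being about group comparisons, n is given per group, and a pooled condition effect does not compare the arms. Two other routes also need inputs the plan does not give. Averaging five uncorrelated measures gives 0.897 but contradicts the correlation of 0.6. Reading 0.80 as Cohen's f (d = 1.6) gives 0.805 exactly, or 0.880 by the normal approximation, but the plan writes d.

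**The consequence is small.** This stands. The analyses are secondary and optional, and the trial's size comes from Aim 1.

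**Stronger readings that the documents do not support:**

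- A reader might infer that this is the only power support for the regional imaging comparisons. It is not. The Hotelling's T-square paragraph states 80% power with 34 subjects for pain responses in three named regions, and the same paragraph as the disputed sentence has a voxel-based estimate for the pain condition. At most, the disputed sentence is the only figure that names pain plus distraction.
- A reader might infer that only 12 per arm will be imaged. No such subset is planned; the schedule has both arms scanned at baseline, weeks 6, 11 and 17, and follow-up.
- A reader might infer that the pilot effects are also out of reach. At 34 per arm they have power above 0.99, and the plan does discount them to 0.80. They remain cross-sectional patient-versus-control differences, not changes due to training.

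**Conclusion.** The figure is wrong as written. For a between-group comparison at d = 0.80 and alpha 0.01, 11 per group gives power of about 0.20 against the stated 0.9, and the conclusion about 12 per group (power about 0.22) names a size that is not this trial's. At the trial's 34 per arm, power is about 0.74, so 0.9 is not reached there either.

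This rests on a two-sample t-test, two-sided; a one-sided test raises 0.20 only to 0.28. The 61% at 27 per arm should not be taken as this trial's settled power, because the plan gives both 34 and 41 per group and does not say how many scans will be analysable. Nothing here shows that enrolment is too small for Aim 1. The voxel-based estimate at 12 per group was not tested, so no conclusion about it follows.

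**What to change.** Replace only the last two sentences of the paragraph: the one that sets alpha 0.01 and d = 0.80, and the one that concludes on 12 per group. In their place, state:

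- With 34 per arm analysed, power for a between-arm d of 0.80 at two-sided alpha 0.01 is about 74%, and the effect detectable with 90% power is d of about 0.96.
- If 20% attrition is applied to 34 (27 analysed, an assumption), power is about 61%; with 41 analysed it would be about 83%. Settle first whether 34 or 41 per group is the intended enrolment.
- The pilot effects compare fibromyalgia patients with controls and do not estimate an effect of resistance training.
- If a within-subject condition effect was intended, say so and give its test, sidedness and correlation.

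Leave the voxel-based sentence as it is. The cost is protocol wording and a less favourable stated power. No procedure, enrolment number or primary analysis changes.
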